6.3.5.2. Laboratory data

Any missing or non-evaluable immunogenicity measurement will not be replaced. The descriptive analysis performed for each assay at each timepoint will exclude participants with a missing or non-evaluable measurement. This is applicable to the standard way of computing geometric mean titers/concentration (GMTs/GMCs)

Computation of GMTs/GMCs from the mixed effects model inherently accounts for the missingness, under the assumption that the missing data are missing at random (MAR). Subject having missing pre-vaccination titer/concentration will be excluded from ANCOVA models (refer Section 4.2.2)

6.3.5.3. Daily recording of solicited events

The following rules are applicable:

- Denominators for the summary of administration site (or systemic) solicited events will be calculated using the number of participants who respond "Yes" or "No" to the question concerning the occurrence of administration site (or systemic) events.
- When a specific solicited event is marked as having not occurred following a specific study dose (i.e. SDTM CE.CEOCCUR=N for the specified post-dose period for the event in question), all daily measurements will be imputed as Grade 0.
- When a specific solicited event is marked as having occurred following a specific study dose (i.e. SDTM CE.CEOCCUR=Y for the specified post-dose period for the event in question), any missing daily recordings will be given imputed values to allow them to contribute to the 'Any' rows but not to specific grade rows of the solicited event summary tables.

The following table shows how participants contribute to each category for a specific solicited event over the Day X to Day Y post-dose period:

Solicited event category	Participants included in the calculation of the numerator
Any	All participants with at least one occurrence of the adverse event at grade 1, grade 2, or grade 3 between Day X and Day Y or with the adverse event marked as present and at least one missing daily recording between Day X and Day Y
At least grade 1	All participants with at least one occurrence of the adverse event at grade 1, grade 2, or grade 3 between Day X and Day Y
At least grade 2	All participants with at least one occurrence of the adverse event at grade 2 or grade 3 between Day X and Day Y
At least grade 3	All participants with at least one occurrence of the adverse event at grade 3 between Day X and Day Y

6.3.5.4. Unsolicited adverse events

Unsolicited adverse event summaries are including serious adverse events unless specified otherwise.

Missing severity, relationship with study vaccine, and outcome of unsolicited adverse events will not be replaced and will appear as 'UNKNOWN' when displayed in a statistical output.

6.3.6. Data derivation

6.3.6.1. Age at vaccination in years and age group

Age will be calculated as the number of years between the year of birth and the year of first vaccination. The age group will be derived based on derived age.

6.3.6.2. Temperature

Temperatures will be presented in degrees Celsius (°C). Temperatures reported in degrees Fahrenheit (°F) will be converted as follows:

Temperature (Celsius) = $((Temperature (Fahrenheit) - 32) \times 5)/9$

6.3.6.3. Numerical serology results

Numerical serology results will be derived from the content of IS.ISORRES in the SDTM dataset. For assays with a specific cut-off, the following derivation rules apply:

IS.ISORRES	Derived value
"NEG", "-", or "(-)"	cut-off/2
"POS", "+", or "(+)"	cut-off
"< value" and value is <= assay cut-off	cut-off/2
"< value" and value is > assay cut-off	value
"> value" and value is < assay cut-off	cut-off/2
"> value" and value is >= assay cut-off	value
"value" and value is < cut-off	cut-off/2
"value" and value is >= cut-off and value is <=ULOQ	value
"value" and value is >ULOQ	ULOQ
All other cases	missing

6.3.6.4. Geometric mean titers/concentrations (GMTs/GMCs)

GMT/GMC calculations are performed by taking the inverse logarithm of the mean of the log titer/concentration transformations. Non quantifiable neutralizing titers/concentrations will be converted as described in Section 6.3.6.3 for the purpose of GMT/GMC calculation. Cut-off values are defined by the laboratory before the analysis.

6.3.6.5. Onset day

The onset day for an event (e.g. AE, concomitant medication/vaccination) is the number of days between the study dose and the start date of the event. This is 1 for an event occurring on the same day as a study dose (and reported as starting after study dose).

6.3.6.6. Duration of events

The duration of an event with a start and end date will be the difference between the start and end date plus one day, i.e., an event that starts on 03MAR2018 and ends on 12MAR2018 has a duration of 10 days.

For solicited administration site and systemic events:

• The duration of a solicited AE with at least one day Grade > 0 is defined as End date(CEENDY) – Start date(CESTDY) + 1, with Start date defined as the first day with the symptom and End date defined as the last day with the symptom in or beyond the solicited period.

- A missing start date will be imputed with the vaccination date.
- For paper diaries, if an ongoing symptom has a missing end date, the end date will be considered equal to vaccination date + 29 days. Partial end dates will be imputed according to Section 6.3.5.1
- The number of days with grade 3 solicited symptom will be defined considering each day with a known grading=3 (for paper CRF, if the max intensity during the ongoing period is 3, each day of the ongoing period will be counted as grade 3).

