6.3.5. Handling of missing data

6.3.5.1. Dates

Element	Reporting Detail		
General Adverse Events	 Partial dates will be displayed as captured in participant listing displays. However, where necessary, display macros may impute dates as temporary variables for sorting data in listings only. In addition, partial dates may be imputed for 'slotting' data to study phases or for specific analysis purposes as outlined below. Imputed partial dates will not be used to derive study day, time to onset or duration (e.g., time to onset or duration of adverse events), or elapsed time variables (e.g., time since diagnosis). The following standard rules will be applied: A missing day will be replaced by 15 A missing day and month will be replaced by June 30th. Partial dates for AE recorded in the CRF will be imputed using the following 		
	Conventions: Missing start day Missing start day and month	If study intervention start date is missing (i.e. participant did not start study intervention), then set start date = 1st of month. Else if study intervention start date is not missing: If month and year of start date = month and year of study intervention start date, then If stop date contains a full date and stop date is earlier than study intervention start date, then set start date= 1st of month. Else, the flag indicating if the event occurred before or after vaccination will be used to complete the date. If 'after vaccination' is selected, the imputed start date will match the vaccine dose given during that month. If 'before vaccination' is selected, the imputed date will be one day before the last vaccine dose given during that month. Else set start date = 1st of month. If study intervention start date is missing (i.e. participant did not start study intervention), then set start date = January 1. Else if study intervention start date is not missing:	

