	Missing end day Missing end day and month Completely missing	 If year of start date = year of study intervention start date, then If stop date contains a full date and stop date is earlier than study intervention start date, then set start date = January 1. Else, the flag indicating if the event occurred before or after vaccination will be used to complete the date. If 'after vaccination' is selected, the imputed start date will match the vaccine dose given during that year. If 'before vaccination' is selected, the imputed date will be one day before the last vaccine dose given during that year. Else set start date = January 1. A '28/29/30/31' will be used for the day (dependent on the month and year) or the study conclusion date whichever comes first. The imputed end date will be the last day of the year (31st of December) or the study conclusion date whichever comes first. No imputation 	
	start/end date	No impatation	

Element	Reporting Detail			
Concomitant	Partial dates for any concomitant medications recorded in the CRF will be imputed			
Medications/Medic		using the following convention:		
al History	Missing start day	If study intervention start date is missing (i.e. participant did not start study intervention), then set start date = 1st of month. Else if study intervention start date is not missing: If month and year of start date = month and year of study intervention start date, then If stop date contains a full date and stop date is earlier than study intervention start date, then set start date= 1st of month. Else, the flag indicating if the event occurred before or after vaccination will be used to complete the date. If 'after vaccination' is selected, the imputed start date will match the vaccine dose given during that year. If 'before vaccination' is selected, the imputed date will be one day before the vaccine dose given during that year. Else set start date = 1st of month.		

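### SAP 6.3.6.6 uses imputed partial end dates for solicited-event duration, which SAP 6.3.5.1 rules out, and its date rules give inconsistent durations

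*SAP*

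**What the plan says.** Protocol 4.1 specifies paper diary cards, so the paper-diary rules in the SAP apply. SAP 4.4.1 plans a table of the duration of each solicited event and a table of days at Grade 3, each with mean, quartiles, minimum and maximum.

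SAP 6.3.6.6 derives these quantities. The duration of a solicited event "is defined as End date(CEENDY) – Start date(CESTDY) + 1". It then gives three date rules and one grade rule:

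- Start: "A missing start date will be imputed with the vaccination date".
- No end date: "if an ongoing symptom has a missing end date, the end date will be considered equal to vaccination date + 29 days".
- Incomplete end date: "Partial end dates will be imputed according to Section 6.3.5.1".
- Grade 3 days: known Grade 3 days count, and for paper records, "if the max intensity during the ongoing period is 3, each day of the ongoing period will be counted as grade 3".

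SAP 6.3.5.1 says: "Imputed partial dates will not be used to derive study day, time to onset or duration". It gives the duration of adverse events as an example of what is excluded. Its adverse-event table nevertheless fills partial end dates. If day and month are missing, "The imputed end date will be the last day of the year (31st of December) or the study conclusion date whichever comes first". If the date is completely missing, the table imputes nothing.

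**The concern.** The duration section borrows its partial-date rule from a section that forbids using the result for duration. It also fills completely missing start and end dates, where the table in 6.3.5.1 leaves them empty. Neither section says which one governs. Two programmers could each follow the SAP faithfully and produce different tables.

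What is at stake is the description of how long reactions last and how many days are severe. For events with incomplete dates, following 6.3.6.6 makes these figures depend partly on how the diary was completed and on the calendar, rather than on the reaction.

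**Working it through.** **1. The formula.** Duration = end − start + 1. The SAP's own example is that "an event that starts on 03MAR2018 and ends on 12MAR2018 has a duration of 10 days": 12 − 3 + 1 = 10. It is reproduced.

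**2. No end date.** Vaccination is Day 1 (SAP 6.3.2), so vaccination date + 29 is Day 30. Solicited onset falls on Days 1 to 4 (Protocol 3.1).

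| Onset | Imputed duration | Observed through Day 4 |
|---|---|---|
| Day 1 | 30 − 1 + 1 = 30 | 4 |
| Day 2 | 30 − 2 + 1 = 29 | 3 |
| Day 3 | 30 − 3 + 1 = 28 | 2 |
| Day 4 | 30 − 4 + 1 = 27 | 1 |

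If the start date is missing too, the result is 30. Under the no-imputation entry in 6.3.5.1, these events would have no duration.

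**3. Partial end date.** I used the adverse-event rows of 6.3.5.1 with onset on Day 1.

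- Month and year known, and equal to the vaccination month: the end becomes the last day of that month, giving 1 to 31 days depending on the vaccination date.
- Only the year known: the end becomes 31 December or study conclusion, if earlier. The interval tables in Protocol 1.3 put the final contact 180 to 210 days after the last dose.
  - Co-Ad, study conclusion first: 180 + 1 = 181 to 210 + 1 = 211 days.
  - Control after dose 1: the second visit comes 30 to 42 days later, so 30 + 180 + 1 = 211 to 42 + 210 + 1 = 253 days.
  - If 31 December comes first, the value can be as low as 1 day (vaccination on 31 December, same year recorded).

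Knowing the year can therefore give a duration about seven times that of knowing nothing (211 / 30 = 7.0), or a far shorter one. The same incomplete field gives a longer value after Control dose 1 only because follow-up is longer there.

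**4. Grade 3 days.** I assume that the ongoing period is Days 5 to 30, and that the paper-record condition refers to the diary card, since the study has an electronic CRF.

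- Ongoing maximum Grade 3: 30 − 5 + 1 = 26 days, plus 0 to 4 days with a recorded Grade 3, so 26 to 30.
- Ongoing maximum Grade 1 or 2: nothing is added.

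SAP 6.3.5.3 takes a different line on missing daily records: they count towards an event of any grade, but not towards a specific grade.

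**5. Effect on the mean (illustration).** The documents give neither a mean duration nor a rate of missing end dates. Assume 250 events, of which k are set to 30 days and the rest average 2.5 days. Mean = ((250 − k) × 2.5 + k × 30) / 250.

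| k | Share | Mean (days) |
|---|---|---|
| 0 | 0% | 2.50 |
| 1 | 0.4% | 2.61 |
| 3 | 1.2% | 2.83 |
| 5 | 2.0% | 3.05 |
| 13 | 5.2% | 3.93 |

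The maximum becomes 30 with a single such event. At these shares the median and quartiles barely move.

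**The case against.** The strongest defence is that 6.3.6.6 is the specific rule for solicited events and overrides a general one. Section 6.3.5.1 also allows imputation for specific analysis purposes, and its table is introduced as covering adverse events recorded in the CRF. On that reading, a completely missing end date has one defined result. This is reasonable for the +29-day sentence, and a reader who infers that this sentence breaches the ban in 6.3.5.1 goes too far: the ban concerns partial dates. The +29-day sentence is at odds only with the no-imputation entry. The defence does not rescue the partial-date sentence, which cites 6.3.5.1 as its authority for a use that 6.3.5.1 excludes.

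A reader might also infer that every ongoing event is given 30 days, or that every ongoing day becomes Grade 3. The text supports neither: later onset gives 27 to 29 days, and the grade rule requires an ongoing maximum of Grade 3. Such days lack a daily grade, but not all grade information.

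The plan also limits how often this should happen. Diaries are checked with the participant and unreturned cards are chased (Protocol 10.3.5.1), and unresolved events are reviewed at later contacts (Protocol 10.3.5.5). A year-only end date should be rare.

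Finally, over-stating reactogenicity can be defended as cautious, and keeping only events with a recorded end date could understate duration if longer events more often lack one. That stands, and it is why the documents do not justify simply deleting the +29-day rule. The year-only rule is not uniformly cautious, however, since it can also shorten the result.

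**Conclusion.** The conflict holds and should be resolved before the tables are produced. It is direct for partial end dates. For completely missing start and end dates it is an unstated exception to the no-imputation entry. Followed as written, 6.3.6.6 gives 27 to 30 days when no end date is recorded, and anything from 1 to about 211 days when only the year is known (up to 253 after Control dose 1). These upper figures assume Day 1 onset and study conclusion on or before 31 December of the recorded year.

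The reach is limited. Only the descriptive duration and Grade 3-day tables change, mainly their mean and maximum. A reader might infer that the safety endpoints are affected; they are percentages of participants with an event, which these rules do not touch, and the primary non-inferiority analysis is untouched. How far the tables would move cannot be stated, because the share of missing end dates is unknown.

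**What to change.** In SAP 6.3.6.6:

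1. Remove the use of 6.3.5.1 partial-date imputation for duration.
2. State whether the +29-day rule, and the imputed start date, are exceptions to 6.3.5.1 for solicited events.
3. Report, by group and dose, the number of events with a missing, partial or imputed end date.
4. Present duration without imputed end dates beside any imputed summary. Alternatively, treat those events as censored and give the median.
5. Show Grade 3 days with a recorded daily grade separately from days assigned from the ongoing-period maximum.

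The cost is SAP wording, a small derivation change and a few extra descriptive rows; data collection does not change. The summary without imputation carries the risk of understatement noted above, so both versions should be shown.

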6.3.6.7. Counting rules for combining solicited and unsolicited adverse events

Unsolicited adverse events with missing administration site flag will be considered systemic.

Solicited events will be coded by MedDRA as per the following codes:

Solicited event	Lower level term code	Corresponding Lower level term decode
Pain	10022086	Injection site pain
Redness	10022061 Injection site erythema	
Swelling	10053425	Injection site swelling
Fever	10016558	Fever
Headache	10019211	Headache
Fatigue	10016256	Fatigue
Myalgia	10028411	Myalgia
Arthralgia	10003239	Arthralgia

Note that these codes might be adapted depending on the current version of MedDRA at the time of analysis.

Multiple events with the same preferred term which start on the same day are counted as only one occurrence.

6.3.6.8. Counting rules for occurrences of solicited events

When the occurrences of solicited events are summarized, each event recorded as having occurred during a specific period will be counted as only one occurrence regardless of the number of days on which it occurs.

The intensity of administration site redness/swelling and fever will be scored as follows:

Intensity grade	Redness/Swelling	Fever
0	≤ 20 mm	< 38.0°C (100.4°F)
1	> 20 - ≤ 50 mm	≥ 38.0°C (100.4°F) - ≤ 38.5°C (101.3°F)
2	> 50 - ≤ 100 mm	> 38.5°C (101.3°F) - ≤ 39.0°C (102.2°F)
3	> 100 mm	> 39.0°C (102.2°F)

6.3.7. Display of decimals

6.3.7.1. Percentages

Percentages and their corresponding confidence limits will be displayed with one decimal except for 100% in which case no decimal will be displayed.

6.3.7.2. Demographic/baseline characteristics statistics

The mean, median, and standard deviation for continuous baseline characteristics (age) will be presented with one decimal.

The minimum and maximum values and quartile values (if required) will be presented with the same number of decimals as the observed values.

6.3.7.3. Serological summary statistics

For each assay, GMTs/GMCs and their confidence limits will be presented with one decimal, as well as GMT/GMC fold increase from pre-vaccination.

GMT/GMC group ratios and their confidence limits will be displayed with 2 decimals regardless of the actual values.

